7.2.5 Study Chair Responsibility for Reporting Adverse Events

All Adverse Events will be reported to regulatory authorities, IRB/IECs and other investigators by the Study Chair in accordance with all applicable local laws and regulations.

8.0 STATISTICAL ANALYSIS PLAN

8.1 Study Statistical Design

This is an open-label, two-stage, single-arm phase 2 study of pembrolizumab plus GM-CSF as $\geq 2^{\text{nd}}$ line therapy for advanced biliary tract cancer. The sample size for Stages 1 and 2 was based on a two-stage Simon's Optimal Design using proportion with PFS at 6 months (%PFS6) as the primary efficacy endpoint. Based upon results of Stages 1 and 2, the study was amended to change primary endpoint to overall response rate (ORR) for overall study with addition of the Expansion Cohort.⁴⁷

8.2 Study Objectives and Hypotheses

See Section 3.

8.3 Definition of Study Endpoints

8.3.1 Primary Endpoint

The primary endpoint was amended to be overall response rate (**ORR**) with addition of Expansion Cohort, based upon the promising responses observed during Stages 1 and 2 (Safety and Efficacy Cohorts). **ORR** is defined as the proportion of subjects with RECIST 1.1-measurable disease at study entry who have a complete response (CR) or partial response (PR) (confirmed + unconfirmed) using RECIST 1.1¹ at any time during the main study. Measurable disease has been added as a required inclusion criterion for Expansion Cohort eligibility. Re-induction and Second Course ORR (rORR, sORR) will be determined based upon response after first dose of re-induction or first dose of Second Course. Subjects with measurable disease at study entry who have unknown or missing response information will be treated as non-responders. Subjects with non-measurable disease at study entry will be excluded from ORR and DOR analyses.

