4.3.6 Rationale for Endpoints

4.3.6.1 Primary Efficacy Endpoint: Overall Response Rate (ORR)

Based upon results from Stages 1 and 2 indicating a promising proportion of patients with durable radiographic and clinical responses, the primary endpoint for this study will be changed to overall response rate (ORR) by locally-assessed RECIST 1.1,¹ previously a key secondary endpoint, and %PFS6 will be changed to a key secondary endpoint. In advanced biliary cancer patients treated with standard 2nd-line chemotherapies, the historical response rate is approximately 10% with short duration of response,^{2,4} and there is no standard therapy approved by the FDA in this context owing to limited efficacy. In unselected advanced biliary cancer patients treated with pembrolizumab monotherapy in KEYNOTE-158, the response rate has not yet been reported. A target ORR of 20% (H_1) on treatment with pembrolizumab plus induction GM-CSF would represent a meaningful improvement in this population, with H_0 5% as null hypothesis in the absence of any established effective standard 2nd line therapy in advanced biliary cancers.

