7.1.5.2 Second Course Pembrolizumab

Subjects who stop pembrolizumab with SD or better may be eligible for up to one year of additional pembrolizumab therapy if they progress within 6 months after stopping study treatment, without any evidence of progression prior to discontinuation, with case-by-case approval from Study Chair and Merck. This retreatment is termed the Second Course of this study and is only available if the study remains open to enrollment and the subject meets the following conditions:

- **Either**

- Stopped initial treatment with pembrolizumab after attaining an investigator-determined confirmed CR according to RECIST 1.1, and:
 - Was treated for at least 24 weeks with pembrolizumab before discontinuing therapy.
 - Received at least two treatments with pembrolizumab beyond the date when the initial CR was declared.

OR

- Had CR, PR, or SD with evidence of clinical benefit (such as minor response radiographically, decline in CA 19-9, and/or improved symptoms) and stopped pembrolizumab treatment after 24 months of study therapy due to protocol-defined treatment duration, without any evidence of disease progression or intolerance.

AND

- Experienced an investigator-determined confirmed radiographic disease progression within 6 months after stopping their initial treatment with pembrolizumab.
- Did not receive any other anti-cancer treatment since the last dose of pembrolizumab.

- Meets original entry criteria in Section 5.1 (with exception of exclusion 19 which is not applicable to re-induction or Second Course).

Subjects who restart treatment will be retreated at the same dose and dose interval as when they last received pembrolizumab. Treatment will be administered for up to one additional year.

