8.4 Sample Size and Accrual Rate

8.4.1 Sample Size

For the primary endpoint of ORR, a sample size of 37 response-evaluable subjects will provide power of 77% with 2-sided 5% alpha and 88% with 1-sided 5% alpha to show ORR improvement from H_0 of 5% to H_1 of 20%, under protocol treatment. Based upon a subset with non-measurable disease enrolled to Stages 1 and 2 before amendment requiring RECIST 1.1-measurable tumors for enrollment to Expansion Cohort, along with potential for dropout in this population with comorbidity of biliary obstruction and liver disease, it is estimated that total enrollment of 42 subjects will include at least 37 response-evaluable subjects.

The key secondary endpoint of %PFS6 was previously the primary endpoint for Stages 1 and 2, prior to amendment adding Expansion Cohort, which also changed to primary endpoint of ORR based upon the promising response rate observed in Stages 1 and 2. For the key secondary endpoint of PFS, an expected overall study PFS-evaluable sample size of at least 40 patients will have power 78% with 2-sided alpha 5% and power 87% with 1-sided alpha to show PFS improvement from H_0 of 20% to H_1 of 40% on protocol therapy.

Pre-amendment, a Simon's 2 stage design was employed to determine if adequate efficacy was observed in Stage 1 to warrant proceeding to Stage 2. The pembrolizumab/GM-CSF combination was considered worthy of additional investigation if the true %PFS6 is 50%, and hence the alternative hypothesis, $\%PFS_1=0.50$. Therefore assuming an α error probability of 5%, and a β error of 20%, the first stage had 9 patients. If ≤ 2 of 9 had been observed progression-free, the study would not proceed to second stage. Since ≥ 3 of 9 patients are observed progression-free at 6 months (4/9 achieved PFS6 in Stage 1), enrollment continued to the second stage with 18 additional patients, with a goal of at least 24 evaluable patients (with planned over-enrollment of 3 additional patients to account for expected 10% dropout rate). If ≤ 9 patients are observed progression-free at 6 months out of 24 evaluable patients by the end of second stage, then no further investigation of the drug is warranted under this PFS6 hypothesis. Conversely, if ≥ 10 patients are progression-free at 6 months among Stages 1 and 2 subjects, the study would be considered positive for the hypothesis: H_0 : $\%PFS_0 < 25\%$ versus H_a : $\%PFS_1 > 50\%$.

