8.6 Planned Analyses

8.6.1 Primary Endpoint Analysis

With expectation of at least 37 subjects with RECIST 1.1-measurable disease evaluable for response, ORR calculated as the proportion with CR + PR (confirmed + unconfirmed) by RECIST 1.1 at any time during the main study. Subjects with measurable disease at study entry who have unknown or missing response information will be treated as non-responders. Subjects with non-measurable disease at study entry will be excluded from ORR and DOR analyses.

For the primary endpoint of ORR, a sample size of 37 response-evaluable subjects will provide power of 77% with 2-sided 5% alpha and 88% with 1-sided 5% alpha to show ORR improvement from H_0 of 5% to H_1 of 20% on protocol treatment, using Fisher's Exact tests. Based upon a subset with non-measurable disease enrolled to Stages 1 and 2 before amendment requiring RECIST 1.1-measurable tumors for study enrollment to Expansion Cohort, along with potential for dropout in this population with comorbidity of biliary obstruction and liver disease, it is estimated that total enrollment of 42 subjects will yield approximately 37 response-evaluable subjects.

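### The primary ORR counts unconfirmed responses in a single-arm, locally read trial with no confirmed-only analysis planned, so one single-scan response can decide the test

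*Combined protocol and SAP*

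**What the plan says.** Section 8.3.1 counts patients with measurable disease "who have a complete response (CR) or partial response (PR) (confirmed + unconfirmed) using RECIST" 1.1. Section 8.6.1 repeats the rule for the analysis: "ORR calculated as the proportion with CR + PR (confirmed + unconfirmed) by RECIST 1.1 at any time during the main study". Patients with measurable disease and missing or unknown response count as non-responders. I found no ORR restricted to confirmed responses, either as a secondary endpoint or as a sensitivity analysis.

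The setting is given in 8.1: "This is an open-label, two-stage, single-arm phase 2 study of pembrolizumab plus GM-CSF". Section 4.3.6.1 specifies local assessment, and 7.1.2.6 has a radiologist or qualified investigator make the measurements, with imaging every 8 weeks on treatment.

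Section 4.3.6.1 explains the move to ORR by "a promising proportion of patients with durable radiographic and clinical responses" in Stages 1 and 2. Section 8.4.1 states that "a sample size of 37 response-evaluable subjects will provide power of 77% with 2-sided 5% alpha and 88% with 1-sided 5% alpha". The null rate there is 5% and the target rate 20%.

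Duration of response (8.3.2, item 4) runs from the first documented CR or PR to progression or death, also without a confirmation requirement.

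**The concern.** One scan that crosses the PR threshold makes a patient a responder for good, even if the next scan does not show it. Patients have repeated chances to cross. At 8-week intervals, the expected median of 6 months on pembrolizumab (1.0) gives about 26/8 ≈ 3 on-treatment scans, and the 24-month maximum about 104/8 = 13. Measurement error can therefore add responders. Under an at-any-time rule, a later scan cannot remove one.

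A randomised comparison would share that error between arms. Here the observed rate is set against a fixed 5%, so spurious responses push the estimate in one direction. With cut-offs of 5 or 6 patients, a single such response can matter, and no planned analysis would show that the result depended on it.

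**Working it through.** **Inputs.** n = 37, null 5%, target 20%, power 77% (2-sided 5%) and 88% (1-sided 5%), all from 8.4.1. Section 8.6.1 describes the test as "using Fisher's Exact tests". For one sample against a fixed rate I used the exact binomial. The plan prints no cut-off, so it has to be inferred.

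**Formula.** P(X ≥ r) = Σ from k = r to 37 of C(37,k) p^k (1−p)^(37−k).

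**Step 1: reproduce the stated power.**

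| Responders needed | Observed ORR | P under 5% | P under 20% |
|---|---|---|---|
| ≥4 | 4/37 = 10.8% | 0.112 | 0.955 |
| ≥5 | 5/37 = 13.5% | 0.036 | 0.888 |
| ≥6 | 6/37 = 16.2% | 0.0095 | 0.778 |

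The smallest r with an upper tail of at most 5% is 5, with power 88.8% (stated 88%). The smallest with an upper tail of at most 2.5% is 6, because 0.036 exceeds 0.025; its power is 77.8% (stated 77%). The plan's figures are reproduced.

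**Step 2: weight of one response.** One patient is 1/37 = 2.7 points. Four confirmed responders plus one unconfirmed moves the 1-sided p from 0.112 to 0.036, which crosses 5%. Five plus one moves it from 0.036 to 0.0095, which crosses 2.5%. This step assumes nothing about how common unconfirmed responses are, but it matters only when the count falls at the boundary.

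**Step 3: possible false-positive inflation.** This needs two assumptions that the documents do not supply: that the 5% null means confirmed responses, and that unconfirmed-only responses add 1, 2 or 3 points to a true confirmed rate of 5%.

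| Rate counted | P(X ≥ 5) | P(X ≥ 6) |
|---|---|---|
| 5% | 3.6% | 1.0% |
| 5 + 1 = 6% | 6.9% | 2.2% |
| 5 + 2 = 7% | 11.4% | 4.2% |
| 5 + 3 = 8% | 17.1% | 7.2% |

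At the cut-off of 6, the 1-point case stays below the nominal 2.5%.

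**Step 4: what a confirmed-only endpoint costs in power.** If 20% already means confirmed responses, nothing changes. If it includes unconfirmed responses and a fraction f fails confirmation (assumed), the confirmed rate is 0.20 × (1 − f).

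| f | Confirmed rate | Power, ≥5 | Power, ≥6 |
|---|---|---|---|
| 0 | 20% | 88.8% | 77.8% |
| 10% | 18% | 82.1% | 67.7% |
| 20% | 16% | 72.7% | 55.5% |
| 30% | 14% | 60.6% | 41.8% |

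**The case against.** The definition is explicit, prespecified and identical in 8.3.1 and 8.6.1. Three further arguments have weight.

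- **The inflation may not exist.** Section 3.1 calls 5% an approximate rate for no treatment. The historical rates of 12% (4.1) and about 10% (4.3.6.1) carry no confirmation status. If the null also includes unconfirmed responses, like is compared with like and the table in step 3 does not apply. A reader might infer that the trial's type I error is known to be inflated; the documents do not support that. They do leave the comparison undefined, which is a gap.
- **Durability is assessed elsewhere.** DOR, PFS, OS and %PFS6 are planned, and a response followed quickly by progression would show as a short DOR. This is partial mitigation. None of these enters the ORR test, and DOR starts at an unconfirmed response. A PR that is lost without progression still accrues duration.
- **Confirmation does not establish durability.** Section 4.3.6.2 describes most historical responses as transient, lasting under 6 months. A response seen on two scans 8 weeks apart and then lost would pass confirmation and still be short. The case for confirmation is therefore protection against single-scan error, not proof of lasting benefit.

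A reader might also infer a contradiction from 7.1.5.2, where one route to Second Course is for a patient who "Stopped initial treatment with pembrolizumab after attaining an investigator-determined confirmed CR according to RECIST 1.1", or from the similar rule in 5.8.1. Those rules govern treatment and retreatment, not the endpoint, and they do not show that the endpoint definition is wrong.

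Finally, this would be a second change to the primary endpoint after results from 9 + 18 = 27 of the 42 planned patients informed the first. That is true, but for a given set of scans a confirmed-only count cannot exceed the current one, so the change is conservative.

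**Conclusion.** The point holds and should be fixed. Three parts rest on the text and exact arithmetic alone: unconfirmed responses count in full, no confirmed-only ORR is planned, and one single-scan response can decide the test at the implied cut-off of 5 or 6 of 37. The cut-offs take n = 37 as planned, and the plan does not say whether the 1-sided or the 2-sided rule decides.

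The false-positive ranges (6.9–17.1% against 3.6%, or 2.2–7.2% against 1.0%) are conditional on both assumptions in step 3. They illustrate sensitivity and are not estimates, since the documents give no count of unconfirmed responses. The stated power is sound for the definition as written. The weakness is in the endpoint definition and in the missing link between that definition and the 5% and 20% rates.

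**What to change.** 1. In 8.3.1 and 8.6.1, define the primary ORR as CR or PR confirmed at a later scheduled scan. Count a response without confirmation, including one with no further scan, as non-response. Keep confirmed plus unconfirmed ORR as a sensitivity analysis.
2. If the sponsor prefers not to change the primary endpoint again, prespecify confirmed ORR as a named analysis reported beside the current one. This is the minimum.
3. State in 3.1, 4.3.6.1 and 8.4.1 whether the 5% and 20% rates refer to confirmed responses, and restate the power if they do not match the chosen definition.
4. Report DOR in confirmed responders.

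**Cost.** No additional imaging is needed, since the 8-weekly schedule already supplies the later scan. The reported ORR may be lower. Responders who leave before the next scan are lost, which matters because 8.4.1 anticipates dropout related to biliary obstruction and liver disease. If 20% includes unconfirmed responses and 10–30% of responders fail confirmation (assumed), power falls from 88.8% to 82.1–60.6% at the cut-off of 5, or from 77.8% to 67.7–41.8% at 6. The minimum option leaves the power of the primary test unchanged.

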8.3.2 Secondary Endpoints

- 1) **Safety** endpoint assessment is described in Section 7.2. The safety endpoints are AEs graded using CTCAE (Version 4.0) criteria. Safety will be assessed by quantifying the toxicities and grades experienced by subjects who have received pembrolizumab plus GM-CSF induction, including SAEs and ECIs. Other safety endpoints include laboratory safety assessments, ECOG performance status, Child Pugh score, vital signs, and physical examinations. The incidence and frequency of dose reduction, treatment delays, and discontinuation for lack of tolerability will be quantified. Re-induction and Second Course safety events will be addressed in the same manner.

- 2) **Tumor PD-L1 status** will be measured by IHC and classified as positive or negative by central laboratory testing (QualTek Laboratories) using pre-specified cut-points.
- 3) A key secondary endpoint is %PFS6 (formerly primary endpoint, changed by amendment with addition of Expansion Cohort). For each patient, PFS will be calculated in days and months from date of first dose of protocol therapy to date of first documented radiographic and/or clinical disease progression or death from any cause. For patients removed from study for other reasons than progression or death, PFS will be censored at the date last known to be progression-free. See Section 5.9 for Replacement policy for non-evaluable patients. The %PFS6 will be calculated as the proportion of evaluable patients progression-free at 6 months. Censored patients without progression will be treated as non-progression statistically and counted in denominator toward %PFS6.

For patients who continue on treatment despite radiographic progression based upon impression of clinical benefit an/or assessment with possible pseudo-progression or a delayed response⁴⁶ (see Section 5.8), PFS will be calculated at time of first documented progression after subsequent imaging confirms progression. If subsequent imaging does not demonstrate progression, then a PFS event will not have occurred and the patient will continue with scheduled imaging assessments per protocol to determine PFS.

Re-induction and Second Course PFS (rPFS, sPFS) will be calculated in months from date of first dose of re-induction or Second Course to date of first documented radiographic and/or clinical disease progression during or after re-induction or Second Course, or death from any cause. RPFS and sPFS will be reported descriptively.

- 4) **DOR** is defined in the subset of subjects with RECIST 1.1-measurable disease at study entry with a CR or PR as the time from first documented evidence of CR or PR until the first documented sign of disease progression or death. Re-induction and Second Course DOR (rDOR, sDOR) will be measured as the time from first documented CR or PR during or after re-induction or Second Course.
- 5) **OS** is defined as the time from the date of first dose of protocol therapy to the date of death due to any cause. Censoring will be performed using the date of last known contact for those who are alive at the time of analysis.

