1.0 TRIAL SUMMARY

[figure not shown]
Abbreviated Title	Pembrolizumab plus GM-CSF Induction in Advanced Biliary Cancers
Trial Phase	II
Clinical Indication	Advanced biliary cancers including unresectable intrahepatic or extrahepatic cholangiocarcinoma and gall bladder carcinoma
Trial Type	Open label, single arm phase II therapeutic clinical trial
Type of control	None
Route of administration	Intravenous (pembrolizumab) and subcutaneous (GM-CSF)
Trial Blinding	N/A
Treatment Groups	N/A (not randomized)
Number of trial subjects	Total enrollment of 42 subjects for expected PFS6-evaluable n=40 and overall response evaluable n=37, combined between the following three cohorts: Stage 1: n=9 (completed) Stage 2: n=18 (completed) Expansion Cohort: n=15
Estimated enrollment period	Stages 1 and 2: 16 months (completed); Expansion Cohort: 12 months
Estimated duration of trial	52 months for accrual plus up to 2 years on treatment from start of treatment of last enrolled patient in the Expansion Cohort, with potential for up to 2 additional years of survival follow up in event that last patient has prolonged stable disease and discontinues without progression after 24 months or 35 cycles
Duration of Participation	Expect median time on pembrolizumab treatment of 6 months

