5.9 Subject Replacement Strategy

See Section 8.6 for definition of analysis populations for safety and efficacy. Approximately 10% over-enrollment is planned to account for possible non-evaluability.

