8.6.2.3 PFS6

Proportion with PFS at 6 months (%PFS6) %PFS6 will be a key secondary endpoint for the overall study. With H_0 %PFS6 of approximately 20% (Section 4.3.6.2) and H_1 %PFS6 of 40% if n=40 are evaluable for PFS6, the power is 78% for 2-sided 5% alpha, or 87% with 1-sided 5% alpha using Fisher's Exact tests.

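### %PFS6 is taken over an undefined evaluable set and censored patients are scored as progression-free, so a patient lost before 6 months without a documented event never counts as a failure

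*Combined protocol and SAP*

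**What the plan says.** Section 8.3.2 item 3 measures PFS for each patient from the first dose of protocol therapy. Radiographic or clinical progression and death from any cause are events. Patients taken off study for any other reason are censored when last known to be progression-free. Measurable disease is not required.

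The same item then defines the rate: "The %PFS6 will be calculated as the proportion of evaluable patients progression-free at 6 months". It adds a pointer: "See Section 5.9 for Replacement policy for non-evaluable patients". The sentence after the definition says that censored patients without progression stay in the denominator and are scored as not having progressed.

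Section 5.9, the target of the pointer, offers only this on replacement: "Approximately 10% over-enrollment is planned to account for possible non-evaluability". Section 8.5.2 defines an evaluable set for ORR alone. No section says who is evaluable for %PFS6.

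Some loss is planned for. The Trial Summary (1.0) gives: "Total enrollment of 42 subjects for expected PFS6-evaluable n=40 and overall response evaluable n=37". For Stages 1 and 2, Section 8.4.1 describes enrollment "with planned over-enrollment of 3 additional patients to account for expected 10% dropout rate".

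The primary endpoint has a different missing-data rule (8.3.1): "Subjects with measurable disease at study entry who have unknown or missing response information will be treated as non-responders".

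**The concern.** Consider a patient who stops treatment in month 2 for a biliary complication, starts another therapy and has no further study imaging. Item 3 supports two treatments of this patient. Called non-evaluable, the patient leaves the denominator. Called censored, the patient stays in and adds a success. Neither route can record a failure, and the two give different rates from the same data.

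Section 8.4.1 links potential dropout in this population to biliary obstruction and liver disease, so loss may well be related to prognosis. %PFS6 was the primary endpoint before the amendment. It remains a key secondary endpoint that objective 3.2(4) sets against a 20% historical rate, so an error in the regimen's favour bears directly on that comparison.

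**Working it through.** **Inputs.** Null rate 20%, alternative 40%, 40 evaluable patients (8.6.2.3); 42 enrolled (1.0). The documents do not give the number of patients lost before 6 months without an event, *d*. I take *d* = 2 from 42 − 40 as an assumption and show 0 to 5.

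**The plan's own figure.** Section 8.6.2.3 states: "With H_0 %PFS6 of approximately 20% (Section 4.3.6.2) and H_1 %PFS6 of 40% if n=40 are evaluable for PFS6", then "the power is 78% for 2-sided 5% alpha, or 87% with 1-sided 5% alpha using Fisher's Exact tests". With X ~ Binomial(40, p):

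- 1-sided 5%: the cut-off is X ≥ 13. P(X ≥ 13 | 0.20) = 0.043 and P(X ≥ 13 | 0.40) = 0.871. The stated 87% is reproduced.
- 2-sided 5% (2.5% in the upper tail): the cut-off is X ≥ 14. P(X ≥ 14 | 0.20) = 0.019 and P(X ≥ 14 | 0.40) = 0.789, against the stated 78%.

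The stated powers are sound. They match the exact one-sample binomial, although the text names Fisher's test.

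**Route A: lost patients kept and scored as progression-free.** If the rate in followed patients is p, the expected reported rate is [p(42 − d) + d] / 42. With 42 in the denominator the 1-sided 5% cut-off is 14, where P(X ≥ 14 | 42, 0.20) = 0.030. With *d* automatic successes, only 14 − d are needed from the 42 − d followed patients, so the type I error is P(Binomial(42 − d, 0.20) ≥ 14 − d).

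| d | Reported rate, p = 20% | Reported rate, p = 40% | Type I error, ≥14/42 rule |
|---|---|---|---|
| 0 | 20.0% | 40.0% | 3.0% |
| 2 | (8 + 2)/42 = 23.8% | (16 + 2)/42 = 42.9% | 8.8% |
| 4 | (7.6 + 4)/42 = 27.6% | (15.2 + 4)/42 = 45.7% | 21.6% |
| 5 | (7.4 + 5)/42 = 29.5% | (14.8 + 5)/42 = 47.1% | 31.4% |

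**Route B: lost patients excluded.** If loss is unrelated to outcome, the expected rate is p and there is no bias. The worst case is that every excluded patient would have failed. With a true 20% in all 42:

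- *d* = 2: apparent rate 0.20 × 42/40 = 21.0%, a shift of 1.0 point. Type I error of the ≥13/40 rule goes from 4.3% to P(X ≥ 13 | 40, 0.210) = 6.1%.
- *d* = 4: apparent rate 0.20 × 42/38 = 22.1%, a shift of 2.1 points. Type I error of the ≥13/38 rule goes from 2.9% to 5.9%.

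Route A, which is what the text prescribes for censored patients, is the larger problem.

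**After the fix: lost patients kept and not counted as progression-free.** With 40% in followed patients:

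- *d* = 0: power 85.1% (≥14/42, 1-sided) or 76.4% (≥15/42, 2-sided).
- *d* = 2: expected rate 16/42 = 38.1%; power P(Binomial(40, 0.40) ≥ 14) = 78.9% or P(Binomial(40, 0.40) ≥ 15) = 68.3%.
- *d* = 4: expected rate 15.2/42 = 36.2%; power 71.0% or 58.7%.

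**The case against.** A reader might infer that no early dropout can ever count as a failure, and that early deaths and rapid decliners disappear from %PFS6. The documents do not support that. Clinical progression and death are PFS events under 8.3.2. Patients who stop without progression remain under disease monitoring (5.8, 7.1.6.4), so progression seen before 6 months still counts. Section 5.6.3 lets removal for palliative radiation be judged clinical progression. The 8.5.2 set cannot be borrowed to argue otherwise: it is written for ORR, requires measurable disease and yields 37 patients rather than 40. Even that set admits patients removed for clinical progression.

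A reader might also infer that dropouts are replaced for this endpoint. Explicit replacement wording appears only for the safety population (8.5.1); for efficacy there is the cross-reference and over-enrollment.

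Other points on that side have weight. The expected shortfall is small, 2 of 42, and its cause is not stated. Section 8.6.2 treats secondary endpoints descriptively, so the type I error figures matter only to the extent that the test in 8.6.2.3 is used. The ORR rule is not a pure contrast, because 8.5.2 removes some unassessed patients before missing responses are counted as failures. Scoring every loss as a failure is conservative rather than unbiased.

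What remains is the patient with no documented event whose monitoring ends early through consent withdrawal, loss to follow-up, new therapy (5.8) or a move to palliative care (7.1.1.5.4). None of these arguments supplies a definition of evaluable or justifies scoring that patient as progression-free at 6 months.

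**Conclusion.** The concern holds for patients lost before 6 months without documented progression or death, and only for them. The plan leaves their handling open between exclusion and success, and both choices can favour the regimen. Scoring 2 such patients as successes adds 3.8 points at a 20% rate in followed patients and nearly triples the 1-sided type I error of a 14-of-42 rule; with 4, the error exceeds one in five. Exclusion of 2 is minor by comparison and harmless if loss is non-informative.

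These sizes rest on an assumed number of losses and on the stated rate applying to followed patients. If no patient is lost in this way, there is no bias. The plan's power figures are not in question.

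**What to change.** Amend 8.3.2 item 3 as follows, and carry the change into 8.6.2.3.

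- Define the %PFS6 denominator as all patients who received at least one dose of protocol therapy (42 if all are dosed).
- Replace the sentence on censored patients: anyone without documented progression-free status at 6 months is not counted as progression-free. Scans every 8 weeks fall at weeks 24 and 32, so state which assessment settles status at 6 months.
- Delete the replacement cross-reference for this endpoint.
- As sensitivity analyses, report the Kaplan-Meier 6-month estimate in all dosed patients and the evaluable-only proportion, with evaluable defined.
- Restate the decision rule and power for the new denominator.

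Changing only the denominator would not be enough, because the censoring sentence would still turn early losses into successes.

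No new data are needed. The cost is a somewhat lower reported rate (38.1% rather than 40% with 2 losses) and lower power: about 79% 1-sided against the stated 87%, and about 68% 2-sided against the stated 78%. The Kaplan-Meier estimate, which uses follow-up up to censoring, shows how much of any difference comes from the conservative rule.
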